## 2. Objectives

Objective 1: To determine the effect of MBSR on abnormal cerebral activation patterns on MEG after stroke. Participants will undergo neuroimaging pre- and post-intervention. We will evaluate differences in activation patterns both at rest and during a visual cognitive task using cluster-based permutation tests. Patients in the MBSR and SSG groups will be compared to one another and to patients with no infarct

(previously collected cohort). T-tests and ANCOVA will be used to determine differences between groups at each time point. Functional connectivity studies will also be performed to evaluate differences between groups.

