- f. There is no concrete definition of treatment failure or removal criteria. We will use an intention-to-treat analysis; however also perform a per-protocol analysis. Attendance at 75% of MBSR or Support Group sessions will constitute full participation.
- g. There will be no change to the patient's care when the study ends. Participants may choose to leave the study at any time. Though they will not be fully compensated (see below) for an early drop-out, their data up to that point will be analyzed, and there will be no alteration in their care.

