## 7. Study Statistics

- a. Primary outcome variables include: MEG- changes in spectral properties and an estimate of the localization of spontaneous brain activity during resting state, functional connectivity during resting state. Clinical- performance on the MOCA and other cognitive measures (as part of the Recovery Study), patient-reported outcomes: fatigue, depression, satisfaction, quality of life.
- b. Secondary outcome variables include: changes in spectral properties, spontaneous brain activity, and functional connectivity during completion of various cognitive tasks.
- c. We will use an intention-to-treat analysis; however, we will adjust for degree of participation and consider an additional exploratory per-protocol analysis. For those lost-to-follow-up, data will be censored at the time they are lost. In addition to the proposed analyses, if there is evidence for an uneven distribution of confounding factors across treatment and control groups, we will perform multivariable linear regression to adjust for confounders (eg. degree of participation, age, sex, level of education, antidepressant use, and major medical co-morbidities (Charlson Comorbidity Index)).

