**To determine the effect of MBSR on abnormal cerebral activation patterns on MEG after stroke:**

- Participants will undergo neuroimaging at 1 and 6 months post-stroke. Participants in the MBSR and SSG will be compared to a previously collected group of controls with no infarct. Source localized whole brain activation will be assessed to determine overall differences in space and time between each group (MBSR v SSG) versus controls for each time point. Cluster-based permutation tests (based on independent measures t values) will then be performed to evaluate mean differences in activation for ROIs between groups at each time point. Paired t values will allow for evaluation of changes over time within each group. Amplitude of peak activation and spike latency will be assessed. ANCOVA will allow for adjustment of potential confounders.
- *Sample Size.* We have been able to demonstrate results at or approaching statistical significance for our current cohort of patients with minor stroke versus controls after enrolling only 9 participants. This number is similar to many other published studies evaluating differences in activation patterns on MEG. We do anticipate less of a difference when comparing stroke patients to other stroke patients, and will therefore increase our sample size to at least 20 individuals in each group. There remains a chance given the potential for improvement in both groups, that we may still be inadequately powered to detect long-term outcomes in this pilot study; however results will also allow treatment effect estimates that will inform a larger clinical trial.

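### The intention-to-treat analysis is to be adjusted for session attendance, a post-randomisation variable, and no as-assigned MBSR v SSG comparison is named as the lead result

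*Combined protocol and SAP*

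**What the plan says.** Section 7, item c, sets the rule for the whole trial: "We will use an intention-to-treat analysis; however, we will adjust for degree of participation and consider an additional exploratory per-protocol analysis". The adjustment carries no condition. Later in the same item a second analysis appears, "In addition to the proposed analyses, if there is evidence for an uneven distribution of confounding factors across treatment and control groups". It is a multivariable linear regression to "adjust for confounders (eg. degree of participation, age, sex, level of education, antidepressant use" and major comorbidity. Participation is thus adjusted for always in one sentence, and only on imbalance in another.

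Section 4, item f, gives a different account: "We will use an intention-to-treat analysis; however also perform a per-protocol analysis". It mentions no participation adjustment and defines the measure: "Attendance at 75% of MBSR or Support Group sessions will constitute full participation". Section 4, item a, puts randomisation before the intervention.

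The comparisons of the two arms are spread over several places:

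- Cognition and PHQ-9 (Section 7): t-tests and chi-square tests at each time point.
- MEG (Section 2, Objective 1): "T-tests and ANCOVA will be used to determine differences between groups at each time point".
- MEG (Section 7): "Cluster-based permutation tests (based on independent measures t values) will then be performed to evaluate mean differences in activation for ROIs between groups", followed by "ANCOVA will allow for adjustment of potential confounders". These confounders are not listed there.

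None of these is called the lead or primary analysis. Section 7, item a, names primary outcome variables but no primary analysis.

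**The concern.** An intention-to-treat estimate answers one question: what difference does assignment to MBSR rather than SSG make? Attendance is a consequence of assignment and of the patient's own state. Patients who are recovering well, less depressed or less tired may attend more, and the two programmes may hold people differently. Conditioning on attendance then compares MBSR and SSG patients who attended equally but who need not have the same prognosis. If attendance is also part of how MBSR works, the adjustment removes part of the effect being sought. Neither result is an effect of assignment, whatever its label.

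This matters because the MEG sample-size paragraph concedes that power may be inadequate and offers treatment-effect estimates for a larger trial as a product of the study. An attendance-adjusted estimate could be carried forward as the intention-to-treat result. Because the adjusted and unadjusted analyses are not ranked, the lead could also be chosen after both are seen.

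**Working it through.** **1. Timing of the covariate.** Randomisation comes first (Section 4, item a), then sessions, and participation is session attendance (Section 4, item f). A confounder of the arm comparison would have to influence assignment. Attendance cannot, although the list in item c places it beside age, sex and education.

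**2. What the adjustment does algebraically.** In a least-squares regression of outcome on arm and attendance,

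adjusted arm effect = difference in mean outcome − γ × (mean attendance in MBSR − mean attendance in SSG),

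where γ is the pooled within-arm slope of outcome on attendance. If γ reflects prognosis, the second term is bias. It vanishes when γ = 0 or when mean attendance is equal.

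*Example (all values assumed).* Attendance has SD 0.15 and correlation 0.5 with a prognostic factor U, and U has loading 0.5 on an outcome with SD 1. Then γ = 0.5 × 0.5 / 0.15 = 1.67 SD per unit of proportion attended. If MBSR attendance is 10 points higher, the shift is −1.67 × 0.10 = −0.17 SD; 20 points higher gives −0.33 SD. Simulation (4,000 trials, 20 per arm) agrees: a true effect of 0.50 SD is estimated as 0.33 and 0.17. With attendance lower in MBSR by 10 and 20 points it is estimated as 0.66 and 0.83. With equal attendance it stays at 0.50.

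**3. Range over a wider set of assumptions.** The only inputs from the documents are 20 per group (the stated minimum) and an 8-week MBSR course, taken as 8 sessions. The rest is assumed:

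- no true effect and outcome SD 1;
- prognostic loading 0.3, 0.5 or 0.7;
- sessions attended binomial, with the log-odds of attending rising by 0.3 to 1.0 per SD of prognosis;
- mean attendance fixed in each arm;
- 20,000 trials per scenario.

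A positive sign favours MBSR when a higher score is better and patients with a better prognosis attend more. Attendance is coded as the proportion of sessions attended.

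| Attendance, MBSR v SSG | SSG sessions | Loading | Bias (SD) | False positives |
|---|---|---|---|---|
| 70% v 85% | 4 or 8 | 0.3 | +0.07 to +0.15 | 5–7% |
| 70% v 85% | 4 or 8 | 0.5 | +0.12 to +0.26 | 6–13% |
| 70% v 85% | 4 or 8 | 0.7 | +0.17 to +0.36 | 8–22% |
| 85% v 70% | 4 or 8 | 0.3–0.7 | −0.06 to −0.36 | up to 22% |
| 80% v 85% | 4 or 8 | 0.3–0.7 | about +0.03 to +0.13 | 5–7% |
| 70% v 85% | 1 | 0.3–0.7 | +0.04 to +0.19 | 5–10% |

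With equal attendance the bias is at most 0.03 SD. If attendance is unrelated to prognosis it is within 0.007 SD of zero. The unadjusted t-test rejects in 4.5 to 5.4% of trials throughout. Coding attendance as 75% reached or not gives +0.06 to +0.25 SD and 5 to 12% for 70% v 85% with 4 or 8 SSG sessions.

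**4. The covariate has no fixed meaning.** SSG is bi-monthly in Sections 1, 4 and 11 and weekly in the pandemic changes at the end; exclusion criterion 6 can be read as weekly. The 75% threshold therefore differs by arm. If every session is attended with probability 0.70:

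- 8 sessions: P(at least 6) = 55%;
- 4 sessions: P(at least 3) = 65%;
- 1 session: P(1) = 70%.

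Equal attendance of 70% under the yes/no rule then gives a bias of up to 0.06 SD (4 SSG sessions) or 0.10 SD (1 session), with false positives at or below about 6%. If participation were instead entered as a count of sessions, it would be tied to arm by design. With 8 v 4 sessions, equal attendance probability, loading 0.5 and no true effect, the adjusted estimate averages −0.64 SD with 25% false positives.

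**The case against.** The strongest reply is that the plan can be read more kindly. The adjustment follows a "however"-type turn and sits beside the exploratory per-protocol analysis, so it may be meant as a supplement. Section 4, item f, has no participation term. The t-tests and chi-square tests for cognition and PHQ-9 cannot carry a covariate, and the regression that lists participation is additional and conditional. It is also only an inference that this list governs the MEG ANCOVA.

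This is a fair reading, and it shows that unbiased comparisons are already planned. But it has to be inferred: the sentence in item c is unconditional, joins the adjustment to the intention-to-treat analysis, and is never ranked below the unadjusted tests.

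On size, the objection is largely right. The 22% figure needs a 15-point attendance gap, loading 0.7, the strongest link between prognosis and attendance, and 8 SSG sessions; with 4 sessions the maximum is about 17%. Exclusion criterion 6 and the payment tied to 75% of sessions push both arms towards high attendance. At 20 per arm the 95% half-width of a mean difference is already 2.02 × √(2/20) = 0.64 SD, so most of these biases are smaller than sampling error. Bias does not average out in a later trial planned on the estimate, however.

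Two neighbouring gaps are separate and would remain. Item a lists many primary outcomes without a primary analysis. The satisfaction and quality-of-life models include mRS and Barthel Index at each time point, which after the intervention are also post-randomisation.

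**Conclusion.** The concern holds. Item c states a rule that, if followed, produces an estimate that is not the effect of assignment, and it attaches the intention-to-treat label to it. That conclusion rests on the plan's own definition and sequence and needs no assumption. The size of the error is unknown, because it depends on how attendance differs between arms and relates to prognosis. Under the assumptions above it runs from essentially nothing to about 0.36 SD in either direction when attendance is coded as a proportion, and the lower part of that range is favoured if attendance is high in both arms. It should be fixed before analysis; the unadjusted comparisons already planned are sound.

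**What to change.** - In Section 7, item c, delete the participation adjustment from the intention-to-treat sentence and remove participation from the confounder list.
- State that the lead intention-to-treat result compares MBSR with SSG as assigned. Any covariates, including those in the MEG ANCOVA, should be named in advance and measured before randomisation.
- Confine attendance to the per-protocol analysis or another analysis labelled exploratory. Reconcile Section 4, item f, where per-protocol is firm, with Section 7, item c, where it is only to be considered.
- Reconcile the SSG frequency across Sections 1, 4, 5 and 11 and the pandemic changes, so that 75% attendance has a clear meaning in each arm.

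The cost is wording only. Attendance is already needed for the 75% rule and the payment schedule, so no new data are required.

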**To determine the impact of mindfulness on post-stroke cognitive impairment:**

- The MoCA and cognitive battery will be administered at 1 and 6 months post-stroke. T-tests and chi square analysis will compare cognitive performance (MoCA, global cognitive score, and individual cognitive tests) pre- and post-intervention for each group (MoCA cutoff <26), and MBSR v SSG participants at each time point.

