**To determine the impact of mindfulness on post-stroke depression:**

- Participants will be administered the PHQ-9 pre- and post-intervention. Paired t-tests will be used to evaluate for significant differences in scores between time points using each score as a continuous variable. Chi square analysis will be used to evaluate presence or absence of moderate depression (PHQ9 score >9). Independent t-tests and chi square analysis will compare scores of MBSR versus SSG participants for each time point.
- *Sample Size.* Based on prior MBSR studies, we anticipate that this will show a greater clinical effect than change in MoCA, giving us more than adequate power to detect differences with this sample size.

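### The MBSR v SSG tests of cognition and PHQ-9 name no baseline-score adjustment, and Section 7c leaves missing post scores undefined and adjusts the ITT analysis for attendance

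*Combined protocol and SAP*

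**What the plan says.** **Between-arm tests.** For cognition, Section 7 states: "T-tests and chi square analysis will compare cognitive performance", both within each group over time and for MBSR v SSG at each time point. For PHQ-9: "Independent t-tests and chi square analysis will compare scores of MBSR versus SSG participants for each time point". Neither paragraph mentions the baseline score.

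**Adjustment elsewhere.** ANCOVA appears for the MEG objective. Section 2, Objective 1: "T-tests and ANCOVA will be used to determine differences between groups at each time point". Section 7, MEG paragraph: "ANCOVA will allow for adjustment of potential confounders". Item 7c adds a multivariable regression if confounders are unevenly distributed. Its list of examples gives degree of participation, age, sex, education, antidepressant use and the Charlson index, but not the baseline outcome score.

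**Losses and attendance.** Item 7c promises intention-to-treat, adjusted for degree of participation, and considers an exploratory per-protocol analysis. It then says: "For those lost-to-follow-up, data will be censored at the time they are lost". Section 4g says of people who leave early that "their data up to that point will be analyzed". Section 4f sets the attendance threshold: "Attendance at 75% of MBSR or Support Group sessions will constitute full participation".

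**Use of the results.** The MEG sample-size paragraph says that "results will also allow treatment effect estimates that will inform a larger clinical trial".

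**The concern.** There are three linked gaps.

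1. Each participant contributes a baseline score, but the randomised comparison of cognition and PHQ-9 does not use it. With about 20 per arm this gives up precision that costs nothing to obtain.
2. Censoring belongs to time-to-event data, and none of these outcomes is of that kind. The sentence therefore does not tell the analyst what to do when a post score is missing.
3. Attendance is observed after randomisation and can depend on the arm. The arms differ in content and perhaps in frequency: MBSR is an 8-week course, while the support group is bi-monthly in Section 4 and weekly in the pandemic section. Once attendance is in the model, the arm coefficient no longer estimates the effect of assignment.

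What is at stake is the between-arm estimate, which the plan intends to carry forward to a larger trial.

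**Working it through.** **The plan's own figure.** Section 7 sets at least 20 per group by analogy with a cohort of 9. It gives no alpha, power, effect size, SD or loss rate, so the figure can be neither reproduced nor called wrong. The checks below assume two-sided 5%, 80% power and SD 1.

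**Step 1: who is in the post-intervention test.** Cognition is scored at 1 and 6 months, and PHQ-9 before and after the intervention. Section 4g keeps data up to the point of leaving. No imputation or mixed model is given. A person lost in between therefore has a baseline score only and leaves the post-intervention t-test or chi-square. A low attender who returns stays in, under the assigned arm. This set is therefore not the per-protocol set at 75% attendance.

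**Step 2: precision with no loss, 20 per arm.**
- t-test, normal approximation: (1.96 + 0.84) × √(2/20) = 0.886 SD. The noncentral t with 38 df gives 0.909 SD.
- ANCOVA: the residual SD is √(1 − r²), where r is the baseline-post correlation (assumed, as the documents give none). The noncentral t uses 37 df.

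| r | √(1 − r²) | Detectable difference, ANCOVA |
|---|---|---|
| 0.4 | 0.917 | 0.834 SD |
| 0.6 | 0.800 | 0.728 SD |
| 0.7 | 0.714 | 0.650 SD |

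At r = 0.6 the residual variance is 1 − 0.36 = 0.64, a fall of 36%. With assumed loss of 20% v 10% (16 and 18 remaining), the t-test detects 0.99 SD and ANCOVA 0.91, 0.80 or 0.71 SD at the same three correlations.

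**Step 3: bias from differential loss.** Let the gap be the mean post score of those observed minus that of those lost. Then

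bias = (MBSR loss × MBSR gap) − (SSG loss × SSG gap).

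Equal loss with equal gaps gives zero. The sign depends on which arm loses more people and whether they were doing worse or better.

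A simulation with no true effect, 20 per arm, r = 0.6, log-odds of loss 1.2 per SD worse and 12,000 runs per cell gave:

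| Loss, MBSR v SSG | Driven by | Bias, t-test | Bias, ANCOVA | Rejection, t-test | Rejection, ANCOVA |
|---|---|---|---|---|---|
| 20% v 20% | either score | 0.00 | 0.00 | 4.8–5.1% | 4.7–4.9% |
| 20% v 10% | baseline | 0.060 | 0.003 | 5.2% | 5.2% |
| 20% v 10% | post | 0.090 | 0.059 | 5.8% | 5.3% |
| 30% v 5% | baseline | 0.137 | −0.002 | 6.5% | 4.9% |
| 30% v 5% | post | 0.229 | 0.152 | 9.8% | 7.8% |

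Biases are in SD units. The Monte Carlo standard error is about 0.003 for bias and √(0.05 × 0.95 / 12,000) ≈ 0.2 percentage points for rejection, so 5.2% cannot be told apart from 5%. When the post score drives loss at 30% v 5%, ANCOVA leaves 0.199/0.235 = 85% of the bias at r = 0.4 and 0.090/0.227 = 40% at r = 0.8.

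**Step 4: attendance as a covariate.** The documents give nothing from which to size this. The point rests on the timing of the variable.

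**The case against.** A reader might infer that the censoring sentence contradicts intention-to-treat, or that it brings in a per-protocol analysis under another name. The documents do not support either reading. Participants with outcomes are analysed as randomised, and missing outcomes can coexist with that principle. The defect is an undefined rule.

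A reader might also infer that the trial's estimate is biased, or biased towards MBSR. That is not shown. Every loss rate and correlation above is assumed, and the direction can reverse. At 20% v 10% loss the bias of 0.06 to 0.09 SD is small beside a t-test sampling SD of 0.335. Clear inflation of the error rate needs something like 30% v 5%, or 6 people against 1. Sections 10 and 11 also work against loss: $100 follows the second MEG, a further $100 rewards full completion including post-intervention cognitive testing, and MEG travel is paid.

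Three further objections stand in part.
- ANCOVA of the post score also drops anyone without one, so it does not turn the analysis into one of all randomised participants.
- Baseline values are not ignored altogether. MEG outcomes are framed as changes, PHQ-9 has paired tests within each arm, and the 7c list is open-ended. But within-arm tests do not answer the randomised question, and an open-ended list that applies only on observed imbalance is not prespecification.
- Section 7 calls this a pilot and admits that power may be inadequate. That argues for a proportionate fix, and for using the baseline score.

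**Conclusion.** The point holds as a request to specify the analysis. The firmest part is precision: at 20 per arm, adjusting for the baseline score lowers the detectable difference from 0.91 SD to between 0.83 and 0.65 SD for assumed correlations of 0.4 to 0.7, even if nobody is lost. Taking degree of participation out of the intention-to-treat analysis is sound on principle, though its effect cannot be sized.

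The missing-data part is weaker. The censoring sentence needs replacing because it defines nothing, but any resulting bias is a risk of unknown size and direction. ANCOVA removes the part of it that the baseline score explains and only some of the part that follows the post score.

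**What to change.** 1. **Section 7, cognition and depression paragraphs.** Replace the post-intervention MBSR v SSG t-tests of continuous cognitive and patient-reported outcomes with ANCOVA of the post score on arm and baseline score. Edit these paragraphs themselves, so that the plan does not name two tests for the same comparison.
2. **Item 7c.** Replace the censoring sentence with: *Participants with a post-intervention score are analysed in their assigned arm, whatever their attendance. Numbers missing and reasons are reported by arm.* Delete degree of participation from the intention-to-treat clause and from the confounder list, and keep it for the exploratory per-protocol analysis.

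The cost is wording. ANCOVA is already a planned method and the baseline scores are already collected. One degree of freedom is spent, and the analysis remains available-case.

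Two additions are optional. One is a sensitivity analysis that imputes missing MoCA and PHQ-9 scores and shifts them in the worse direction, one arm at a time. With 20% loss in an arm, shifts of 0.5 and 1.0 SD move that arm's mean by 0.20 × 0.5 = 0.10 and 0.20 × 1.0 = 0.20 SD. The other is a minor clarification of item 7d: a participant who cannot tolerate MEG or MBSR stops that procedure only, and clinical outcomes are still collected.

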**To determine the effect of MBSR on abnormal cerebral activation patterns on MEG after stroke:**

- Participants will undergo neuroimaging at 1 and 6 months post-stroke. Participants in the MBSR and SSG will be compared to a previously collected group of controls with no infarct. Source localized whole brain activation will be assessed to determine overall differences in space and time between each group (MBSR v SSG) versus controls for each time point. Cluster-based permutation tests (based on independent measures t values) will then be performed to evaluate mean differences in activation for ROIs between groups at each time point. Paired t values will allow for evaluation of changes over time within each group. Amplitude of peak activation and spike latency will be assessed. ANCOVA will allow for adjustment of potential confounders.
- *Sample Size.* We have been able to demonstrate results at or approaching statistical significance for our current cohort of patients with minor stroke versus controls after enrolling only 9 participants. This number is similar to many other published studies evaluating differences in activation patterns on MEG. We do anticipate less of a difference when comparing stroke patients to other stroke patients, and will therefore increase our sample size to at least 20 individuals in each group. There remains a chance given the potential for improvement in both groups, that we may still be inadequately powered to detect long-term outcomes in this pilot study; however results will also allow treatment effect estimates that will inform a larger clinical trial.

